6.2 Consenting Procedures

The study team will broadcast the study notification to all new admissions by placing a poster at the common areas of the facility as well as a copy of the broadcast study notification within the standard admissions paperwork (this provides a way for the patient or their legally authorized representative to receive a written statement of the research). The use of the broadcast study notification as well as the proposed broadcast study notification statement/flyer (included in this submission) has been approved by Acts (the participating nursing home). The broadcast notification will serve both as an advertisement and information sheet.

Study team members will consult virtually with Acts staff to determine eligibility and contact recently admitted potential participants via telephone. If the potential participant meets eligibility criteria, study team members will contact potential participants (eligible patients or the LAR/surrogate decision makers of eligible patients) by phone to explain the purpose of the study. The study team members will read the broadcast study notification to all subjects with the option to opt out.

Study team members can confirm that the individual is the LAR because we have been given the contact information by a designated Acts staff member who is involved in the resident's admission and overall care. The study team member asks the designated person at Acts if the resident can make their own decisions.

6.3 Data Collection

Baseline data will be collected virtually via telephone by asking each newly admitted patient or their LAR/surrogate to complete the Patient Outcomes Scale (POSv2) as well as two ADRD specific evaluations: the Satisfaction with Care at the End of Life in Dementia (SWC-EOLD) and the Symptom Management at the End of Life in Dementia (SM-EOLD).

Follow-up visit data will be collected virtually via telephone as well. The patient or surrogate/LAR will complete the POSv2, SWC-EOLD, and SM-EOLD 14-21 days post baseline measures.

6.4 Measures and Instruments

To establish feasibility, benchmarks for success will be measured. To measure quality of life, the Palliative Outcomes Scale (POSv2) will be used. To assess care satisfaction and symptom management, the Satisfaction with Care at the End of Life in Dementia (SWC-EOLD) and the Symptom Management at the End of Life in Dementia (SM-EOLD) surveys will be used.

Table 3 provides an outline of the outcome measures.

6.5 Table 3 Study Measures

Construct	Measure/ Description
Primary Outcomes: Baseline, 14-21 days	
Patient/Caregiver Quality of Life	Palliative Outcomes Scale version 2 (POSv2): A 12 item survey that measures quality of life in five dimensions: 1) physical; 2) emotional; 3) psychological; 4) spiritual needs, and 5) provision of information and support. Items scored on a 5-point Likert Scale (0=not at all, 4= overwhelmingly) based on symptom/need in the past week. Overall profile score is calculated by summing responses to the 10 questions (range 0-40).
Secondary Outcome: Baseline, 14-21 days	

Satisfaction with Care	Satisfaction with Care at the End of Life in Dementia (SWC-EOLD): A validated, 10-item scale that measures caregiver satisfaction with care for persons with dementia. Each item is measured on a 4-point Likert scale ranging from 1 (“strongly disagree”) to 4 (“strongly agree”). Specific elements include satisfaction with medical and nursing care, decision-making, and their understanding of the persons with dementia illness. All items are summed, yielding a range of scores of 10-40. Higher scores indicate greater satisfaction.
Symptom Management	Symptom Management at the End of Life in Dementia (SM-EOLD): A valid and reliable 9 item scale administered to a caregiver that measures persons with dementia physical and psychological symptoms. Each item is rated on a 6-point Likert scale ranging from 0 to 5 (0 = “daily”, 1 = “several days a week”, 2 = “once per week”, 3 = “2 or 3 days a month”, 4 = “once a month”, 5 = “never”). Scores are summed and range from 0 to 45. Higher scores indicate better symptom management.

7 SAFETY MONITORING

7.1 Data Safety Monitoring Plan

The investigator will permit all study-related monitoring, audits, and inspections by the IRB and regulatory bodies. Participation as an investigator in this study implies acceptance of potential inspection by regulatory authorities. The PI will ensure the trial is conducted according to the approved protocol and be responsible for carrying out the DSM Plan. The PI will monitor the data safety monitoring plan and will submit an annual report to the UMB IRB.

7.2 Adverse Events and Serious Adverse Events

The study is low risk because it reflects current best practices for palliative care in the nursing home setting. We do not anticipate any adverse reactions to the intervention and therefore minimal risks to participants is expected. For Acts staff participating in the palliative care encounter training there is no risk. Adverse events (AEs) are defined as “unanticipated problems” involving risks to study participants or others (<https://grants.nih.gov/grants/guide/notice-files/not99-107.html>). AEs will be identified by study staff through participant self-report, routine study assessments, or through interactions with participants or SNF nursing home staff. Because this proposal involves an evidence-based palliative care intervention provided by specialty trained Nurse Practitioners, no serious adverse events are expected to occur. However, the following may occur and expected in persons with serious illness:

- Death, Hospitalization, Change in clinical status

Adverse Event (AE): AE is any untoward or unfavorable medical occurrence in a human study participant, including any abnormal sign (e.g., abnormal physical exam or laboratory finding), symptom, or disease, temporally associated with the participants’ involvement in the research, whether or not considered related to participation in the research.

Serious Adverse Event (SAE): SAEs consist of any adverse event that results in death; is life threatening or places the participant at immediate risk of death from the event as it occurred;

requires or prolongs hospitalization; causes persistent or significant disability or incapacity; results in congenital anomalies or birth defects; is another condition which investigators judge to represent significant hazards

Any SAE will be reported to the IRB as soon as possible but no later than 5 calendar days. If AEs or SAEs are identified or reported, the PI will convene an immediate (within 48 hours) ad hoc meeting with the study team. During this meeting, we will determine the relevance and significance of the AE to the study, including an aggregate analysis of other occurrences of the same (or similar) event. Then we will determine if the AE can be determined to be an anticipated or unanticipated problem (evaluate whether or not the event would have likely happened regardless of participation in the study) involving risk to human subjects or a serious adverse event and determine what, if any, follow-up is needed with the participant/family surrogate, participant's primary care team, and the nursing facility leadership and staff. AEs will be monitored on an ongoing basis by the research assistant and/or the project manager. A listing of AEs and their attribution (e.g., level of probability of being study related, intervention related, or unrelated to study or treatment) will be recorded and reviewed with each AE.

Data needing to be reported:

- The date the adverse event occurred
- The adverse event
- Relationship of the adverse event to intervention
- If the AE was expected
- The severity of the AE
- The intervention
- Detailed text that includes the following information:
 - An explanation of how the AE was handled
 - A description of the subject's condition
 - Indication if the subject remains on the study
 - If an amendment will need to be made to the protocol and/or consent form
 - If an amendment will need to be made to the protocol and/or consent form

The PI's signature and the date it was signed are required on the completed report.

7.3 Assessment of External Factors Related to AEs

The study team will track literature reports, developments in palliative care, and results of related studies that may have an impact on the safety of participants or on the ethics for this research study.

8 PARTICIPANT WITHDRAW/DISCONTINUATION

Subjects remain free to refuse the Palliative Care encounter (e.g., "SNF-PC") and/or any care or therapies offered because of said consultation. Subjects may withdraw voluntarily from participation in the study at any time and for any reason. Participants should continue to be followed for 30 days, with their permission, even if the study intervention is discontinued.

8.1 Study Discontinuation

The study may be discontinued at any time by the IRB, the NINR, the OHRP, or other government agencies as part of their duties to ensure that research participants are protected.

9 STATISTICAL CONSIDERATIONS

9.1 General Design Issues

N/A

9.2 Sample Size and Randomization

The primary outcome is to establish the feasibility of the post-acute Skilled Nursing Facility (SNF) Palliative Care (PC) intervention for patients with Alzheimer's disease and related dementias (ADRD) and cognitive impairment (CI). Following guidelines on sample size selection for pilot studies we focused on the corresponding precision (widths of confidence intervals [CIs]) of our estimates of feasibility to assess sample size. With 25 participants per group, 90% CIs for proportions will be $\pm 10-16\%$ for within-group proportions between 10-90%, which is sufficient precision for a pilot under a wide range of possible outcomes. Another primary outcome of the study is to estimate effect sizes for the SNF-PC intervention on patient/family caregiver reported satisfaction with care, symptom management, and quality of life. Based on our current experience in the parent study, we anticipate up to 10% of participants will not have outcomes available (e.g., missing data or dropout).

Based on prior results and a conservative assumption of a modest correlation ($r = 0.3$) between pre- and post-intervention values, we estimate the corresponding standard deviation (SD) of pre-post changes of the Satisfaction with Care at the End of Life in Dementia (SWC-EOLD) scale to be 4.9 units. With 25 participants enrolled per group (22 with complete data), we will have 80% power to detect a change in SWC-EOLD within the intervention group of 2.7 scale units at a two-sided significance level of $\alpha = 0.1$, which corresponds to a clinically significant change. The precision of the mean changes in SWC-EOLD within group and between groups (90% CIs) would be ± 1.0 and ± 2.5 scale units, respectively. Lastly, with this sample size, the upper bound of the one-sided 90% CI for the SD of each endpoint will be only 17% higher than the point estimate, so there will be limited sample size inflation needed when powering a follow up study based on the SD estimates from the proposed study

This is a non-randomized pragmatic clinical trial.

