The goal of the intervention is to prevent, identify and treat symptoms early during SNF care, establish goal directed treatment decisions, and support the patient and family in decision making. We anticipate that many Palliative Care encounters involve a single encounter with the patient and/or LAR/surrogate decision maker, but we have made allowances for follow up visits depending on individual patient and family needs (e.g., symptom management, continuing goals of care discussions). We will use usual care as the control condition. Usual care consists of traditional resources focused on skilled nursing care without services to support specialty palliative care. A usual care comparison will test whether the Palliative Care Encounter improves patient/family reported outcomes compared to traditional services. We have chosen to not use an attention control condition because the goal of this pilot clinical trial is to assess feasibility and determine the effect size of the intervention on the primary outcome.

Study team members will collect measures via phone or through a secured online template to minimize missing data at two time points (baseline and 14-21 days later) during the study. All data will be entered and managed in REDCap by the RA, project manager, or the PI.

Patient/Caregiver Quality of Life: Measured at baseline and follow-up (14-21 days later), the Palliative Outcomes Scale version 2 (POSv2) is a 12-item survey that measures quality of life in five dimensions: 1) physical; 2) emotional; 3) psychological; 4) spiritual needs, and 5) provision of information and support. (RESEARCH PROCEDURE)

Satisfaction With Care at the End of Life in Dementia (SWC-EOLD): Measured at baseline and follow-up (14-21 days later), the SWC-EOLD is a validated, 10-item scale that measures satisfaction with care for PLWD. Each item is measured on a 4-point Likert scale ranging from 1 (“strongly disagree”) to 4 (“strongly agree”) and uses a “prior 90 days” timeframe. Specific elements include satisfaction with medical and nursing care, decision-making, and their understanding of illness. All items are summed, yielding a range of scores of 10-40. Higher scores indicate greater satisfaction. (RESEARCH PROCEDURE)

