9.4 Data Analyses

We will establish the feasibility of the SNF-PC intervention in persons with ADRD/CI using established benchmarks based on published recommendations for evaluating pilot studies. We will track the number of eligible patients, monitor follow-up, document rates of eligibility, enrollment, and completion of the intervention, and collect the outcome measures with <5% missing data. We will determine clinician fidelity to the SNF-PC protocol

We also will estimate the effect size of the SNF-PC intervention on pre-post changes in the POSv2, SWC-EOLD, and the SM-EOLD relative to the control group. These estimates will be summarized with two-sided 90% Confidence Intervals and p-values corresponding to tests against the null hypothesis of no (zero) difference.

We also will examine the demographics, clinical characteristics, and palliative care needs of people with ADRD/CI versus non ADRD/CI serious illnesses during post-acute SNF care. As the

comparisons will be made using baseline/pre-intervention information, all 50 participants enrolled in this study are potentially includable in the analysis.

The primary analysis will be to compare the mean pre-post changes in the POS v2 between the intervention and control arms. Linear regression models will be used to compare the two groups. The within-arm changes and differences between arms will be summarized with two-sided 90% CIs and p- values corresponding to tests against the null hypothesis of no (zero) change or difference. We will also explore subgroup effects of the intervention on endpoints by testing for statistical interactions between the binary group indicator and covariates of interest such as sex, age, and race.

Other key parameters needed to plan a follow-up study will be estimated as well, including the standard deviation (SD) and intraclass correlation coefficient (ICC) of each endpoint. The ICC summarizes the degree of correlation of values among patients within a site, which is an important parameter when planning a future cluster randomized controlled trial.

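### Section 9.2 gives all three scales primary status, against Table 3 and 9.4, and its only power figure does not describe the primary POSv2 comparison

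*Combined protocol and SAP*

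**What the plan says.** Section 9.2 names feasibility as the primary outcome and bases the sample size on it: "we focused on the corresponding precision (widths of confidence intervals [CIs]) of our estimates of feasibility to assess sample size". It then adds "Another primary outcome of the study is to estimate effect sizes for the SNF-PC intervention", and the sentence goes on to list satisfaction, symptom management and quality of life together.

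The one power statement is "80% power to detect a change in SWC-EOLD within the intervention group of 2.7 scale units", at two-sided alpha 0.10, with an SD of change of 4.9 and 22 completers per group. Precision of mean change follows for the same scale only: "The precision of the mean changes in SWC-EOLD within group and between groups (90% CIs) would be ± 1.0 and ± 2.5 scale units".

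Section 9.4 says: "The primary analysis will be to compare the mean pre-post changes in the POS v2 between the intervention and control arms". It also plans within-arm summaries: "The within-arm changes and differences between arms will be summarized with two-sided 90% CIs", with p-values. Between-arm p-values are planned for all three scales.

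Table 3 (section 6.5) has POSv2 alone under its primary heading. SWC-EOLD and SM-EOLD stand under "Secondary Outcome: Baseline, 14-21 days". Section 6.1 speaks of one primary outcome: "the goal of this pilot clinical trial is to assess feasibility and determine the effect size of the intervention on the primary outcome".

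**The concern.** There are two linked problems in section 9.2.

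- **Status of the scales.** The clause on effect sizes puts SWC-EOLD and SM-EOLD on the same footing as POSv2. Table 3 and 9.4 do not. A favourable SWC-EOLD or SM-EOLD result could be called primary by citing 9.2 and secondary by citing Table 3. Because 9.4 plans a p-value for each scale, that freedom raises the chance of a false positive.
- **Power and precision.** The 80% matches the primary analysis in neither endpoint nor contrast. The only between-arm figure, ±2.5, is for SWC-EOLD. The one precision figure in 9.2 that reaches POSv2 is the 17% bound, which concerns the SD of each endpoint and not a mean change. Yet the pilot is meant to determine the effect size on the primary outcome, and a reader cannot tell how precisely that will be done.

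**Working it through.** **Inputs from section 9.2:** SD of SWC-EOLD change 4.9; pre-post correlation r = 0.3; 22 completers per arm; two-sided alpha 0.10; within-arm change of 2.7 units. The documents give no SD of change for POSv2, so its figures can be stated only in SD units.

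**1. The plan's own power figure.** One-sample t on change scores: SE = 4.9/√22 = 1.045, noncentrality 2.7/1.045 = 2.58, 21 df. Power = 80.4%. The stated 80% reproduces.

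**2. The plan's own precision figures.**
- Between arms: SE = 4.9 × √(2/22) = 1.477; half-width = t(0.95, 42 df) × SE = 1.682 × 1.477 = 2.48. The stated ±2.5 reproduces.
- Within arm: half-width = t(0.95, 21 df) × SE = 1.721 × 1.045 = 1.80. The stated ±1.0 does not reproduce; it is close to the standard error.

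**3. The between-arm contrast, unadjusted and not accounting for site** (noncentral t, 42 df).
- Half-width in SD units: 1.682 × √(2/22) = 0.51 SD of change.
- Difference detectable with 80% power: 0.76 SD, which for SWC-EOLD is 0.762 × 4.9 = 3.7 units.
- If the within-arm 2.7 units is assumed to serve also as a between-arm target (the documents give none), power is 56%.

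**4. The same contrast adjusted for baseline.** Section 9.4 specifies linear regression but lists no covariates for it. Single-time SD implied by 9.2, assuming equal variances = 4.9/√(2 × (1 − 0.3)) = 4.14. Residual SD = 4.14 × √(1 − 0.3²) = 3.95. Half-width = t(0.95, 41 df) × 3.95 × √(2/22) = 1.683 × 1.191 = 2.0 units. Power for 2.7 units is about 72%.

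**5. False positives if any of three scales may count as primary**, each tested at two-sided 0.10 under no effect. Independence gives 1 − 0.95³ for favourable results and 1 − 0.9³ for either direction. The correlated rows are simulated trivariate normal results; the correlations are assumptions.

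| Common correlation | At least one favourable | At least one in either direction |
|---|---|---|
| 0 | 14% | 27% |
| 0.3 | 13% | 26% |
| 0.5 | 12% | 24% |
| 0.8 | 9% | 18% |
| One scale only | 5% | 10% |

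**The case against.** The strongest reply is that this is a pilot. Its size rests on the precision of feasibility proportions, no success rule depends on a p-value, and 9.4 already names one primary analysis. The 80% sentence says plainly which scale and contrast it covers, and 9.4 does plan within-arm tests. All of this stands, and it limits the point to consistency and disclosure within 9.2.

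Some stronger readings are tempting, but the documents do not support them:

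- **That the 80% is wrong or the trial too small.** The figure is right for what it describes, and the sample size is not derived from it.
- **That the primary comparison has 56% power.** That figure carries a within-arm SWC-EOLD change over to a between-arm comparison, for which the documents set no target. Baseline adjustment would raise it to about 72%.
- **That site clustering lowers power further.** The documents do not say how arms are allocated across the 11 sites. If both arms exist within sites, accounting for site need not widen the interval and may narrow it. No clustering figure is offered here.
- **That the chance of a spurious positive claim is 18% to 27%.** That range counts apparent harm as well as benefit. For favourable results it is 9% to 14%.
- **That the documents conflict throughout on what is primary.** Table 3 and 9.4 agree, and 6.1 is compatible with them. Section 1.1 lists the three constructs under a primary objective only as things to be measured, and such an objective can contain primary and secondary outcomes. The conflict lies in one clause of 9.2.

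**Conclusion.** The point holds in this limited form. Section 9.2 contradicts Table 3 and 9.4 on the status of SWC-EOLD and SM-EOLD, and it gives neither power nor mean-change precision for the primary POSv2 comparison.

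The contradiction would let the chance of a favourable false positive rise from 5% to between 9% (assumed correlation 0.8) and 14% (independence). The SD-unit figures for the between-arm comparison need only 22 completers per arm, an unadjusted analysis of change and no allowance for site. The SWC-EOLD figures also use the plan's SD of 4.9, and the baseline-adjusted ones its r = 0.3. This should be corrected, but it is no reason to change the sample size or the design.

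**What to change.** Edit section 9.2 only.

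1. Replace the clause that makes effect sizes on all three scales a further primary outcome. After feasibility, name POSv2 as the primary patient/caregiver-reported outcome and SWC-EOLD and SM-EOLD as secondary, as in Table 3 and 9.4.

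2. Beside the ±2.5, add:

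> The 80% within-group power does not apply to the primary between-arm comparison. With 22 completers per arm, an unadjusted between-arm comparison of change, not accounting for site, has a 90% CI half-width of about 0.51 SD of the change score and 80% power for about 0.76 SD (for SWC-EOLD, ±2.5 and 3.7 units). Adjustment for the baseline score would improve this (for SWC-EOLD with r = 0.3, about ±2.0 units).

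   If the sponsor has an SD of change for POSv2, give the figures in POSv2 units as well.

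3. In the same edit, correct the within-group ±1.0 to about ±1.8 (n = 22).

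The cost is wording: no extra patients, visits or data. The stated power picture becomes less favourable, and SWC-EOLD and SM-EOLD can no longer be reported as primary.

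### Section 9.2 gives the within-group 90% CI for SWC-EOLD change as ±1.0, but its own SD and number of completers give about ±1.8

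*Combined protocol and SAP*

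**What the plan says.** Section 9.2 (Sample Size and Randomization) plans the SWC-EOLD analysis from pre-post changes whose SD it takes "scale to be 4.9 units", a value that already reflects the assumed pre-post correlation of 0.3. On missing data, "we anticipate up to 10% of participants will not have outcomes available". The calculation then proceeds as follows: "With 25 participants enrolled per group (22 with complete data", and "we will have 80% power to detect a change in SWC-EOLD within the intervention group of 2.7 scale units" at a two-sided alpha of 0.1. The next sentence turns to precision: the mean changes "within group and between groups (90% CIs) would be ± 1.0 and ± 2.5 scale units, respectively".

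Section 9.4 (Data Analyses) fixes the type of interval: "The within-arm changes and differences between arms will be summarized with two-sided 90% CIs".

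**The concern.** With equal arms and a common SD, the between-group half-width is √2 × t(2n−2)/t(n−1) times the within-group one. Since t(2n−2) is smaller than t(n−1), that ratio cannot exceed √2, about 1.41. The stated pair has a ratio of 2.5/1.0 = 2.5, so the two figures cannot both come from one SD and one arm size, whatever values are chosen.

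Section 9.2 justifies the sample size by the width of confidence intervals and lists effect sizes for satisfaction with care among the things to be estimated. A within-group half-width that is too small tells readers, including anyone planning the follow-up study, that the pilot will measure change within an arm more precisely than it can.

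**Working it through.** **Inputs, all from section 9.2 except the last**

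- SD of pre-post change in SWC-EOLD: 4.9
- Per arm: 25 enrolled, 22 complete (25 × 0.9 = 22.5, taken as 22)
- Two-sided alpha 0.1, power 80%, detectable change 2.7
- CI level 90%; two-sided according to section 9.4

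**Step 1. Do the neighbouring figures reproduce?**

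- Power for a 2.7-unit within-group change (one-sample noncentral t, n = 22, two-sided alpha 0.1): 0.804. The change detectable with 80% power is 2.685. Stated: 80% for 2.7. Agrees.
- Between-group half-width: t(0.95, 42) × SD × √(2/n) = 1.682 × 4.9 × √(2/22) = 2.485. Stated: 2.5. Agrees.
- One-sided 90% upper bound for the SD: √(df/χ²(0.10, df)) = 1.168 with the two arms pooled (df = 42). Stated: 17% above the estimate. Agrees on that pooled basis.

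SD 4.9 and 22 per arm are therefore the inputs that the paragraph uses.

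**Step 2. The within-group half-width**

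- Standard error: 4.9/√22 = 1.045
- Half-width: t(0.95, 21) × SE = 1.721 × 1.045 = **1.80**. Stated: 1.0. Does not agree.

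**Step 3. Two cross-checks from the plan's own figures**

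- At n = 22 and alpha 0.1, the detectable change is 2.685/1.798 = 1.494 times the 90% half-width. The stated 2.7 implies 2.7/1.494 = ±1.81. A half-width of ±1.0 would imply a detectable change of 1.0 × 1.494 = 1.49.
- The between-group ±2.5 implies about 2.5/√2 = ±1.77 within group.

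**Step 4. Other readings, SD 4.9**

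| Reading | Half-width |
|---|---|
| n = 22, t | 1.80 |
| n = 22, z | 1.72 |
| n = 25, t | 1.68 |
| n = 25, z | 1.61 |
| n = 22, one-sided 90% multiplier, t / z | 1.38 / 1.34 |
| Both arms pooled, n = 44, two-sided, t | 1.24 |
| Both arms pooled, n = 50, two-sided, t | 1.16 |
| Both arms pooled, n = 44, one-sided multiplier, t | 0.96 |

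Only the first four rows are two-sided 90% intervals within one group; they run from 1.61 to 1.80.

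**Step 5. What ±1.0 would require**

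- At SD 4.9: about 67 completers in the arm (t), or 65 (z).
- At 22 completers: an SD of about 2.7 (t) to 2.9 (z).
- At SD 4.9 and 22 completers, ±1.0 covers about 65%.

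**Step 6. An example.** An observed mean change of 2.7 would have a 90% CI of 2.7 ± 1.80, or 0.90 to 4.50. The stated figure suggests 2.7 ± 1.0, or 1.7 to 3.7. Both exclude zero, but the lower limit is well under 1 unit closer to zero than planned only in the second case's favour: 0.9 against 1.7.

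**The case against.** The best counter-argument concerns weight. Table 3 lists SWC-EOLD as a secondary outcome, the primary analysis in section 9.4 is the between-arm comparison of POSv2 change, and no benchmark or decision rule uses ±1.0. The feasibility precision of ±10–16% is a separate statement. All this is true and limits the consequence. It does not make the figure incidental, because section 9.2 also calls the estimation of effects on satisfaction with care a primary outcome and argues from CI width.

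The two-sided sentence in section 9.4 stands in a paragraph that opens with POSv2, and the sentence there that names SWC-EOLD speaks of effects relative to control. Applying the two-sided within-arm interval to SWC-EOLD is thus a reasonable inference, not an explicit statement. The result does not depend on it: a one-sided multiplier at n = 22 still gives 1.34 to 1.38.

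One reading does round to 1.0: both arms pooled with a one-sided multiplier (0.96). It is not within group, and it does not fit the adjacent ±2.5, which needs the two-sided multiplier.

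A different SD does not help either. The raw-score SD implied by r = 0.3 is 4.9/√(2 × 0.7) = 4.14, giving 1.721 × 4.14/√22 = 1.52. Adjustment for baseline gives a residual SD of 4.14 × √(1 − 0.3²) = 3.95 and a half-width of 1.721 × 3.95/√22 = 1.45, and it would move the between-group figure to about 2.0.

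A digit misread when the PDF was converted to text cannot be strictly excluded. Nothing points to one, and a look at the PDF page would settle it.

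**Conclusion.** The concern holds. On the plan's own inputs (SD of change 4.9, 22 completers, two-sided 90%), the within-group half-width is ±1.80, against ±1.0 stated. Allowing z for t, or 25 patients for 22, the range is ±1.61 to ±1.80, about 60–80% above the stated value. The stated figure is close to the standard error (1.04 at n = 22, 0.98 at n = 25), so an omitted multiplier is the likely cause; the document does not confirm it.

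The consequence is confined to this one precision statement. The 80% power claim and the between-group ±2.5 are right as written, and nothing in the design or analysis rests on ±1.0.

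**What to change.** In section 9.2, replace ±1.0 with ±1.8 and leave ±2.5 as it is. The value ±1.8 uses the t multiplier and the 22 completers that the section assumes. If the plan were instead to rely on the target of under 5% missing data in section 9.4 (25 × 0.95 = 23.75, about 24 completers), the figure would be ±1.71 (t) or ±1.65 (z), and the text should then name that basis. The cost is one number, with no change to design, sample size, power statement or analyses.
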